9.3.2. Concomitant and Prior Medications other than Anti-PD Medications

Prior and concomitant medications other than anti-PD medications will be coded to a preferred name according to the WHODRUG coding dictionary version 2015:03 or higher. The number and percent of subjects will be summarized for prior and concomitant medications for each preferred term (PT) in the FAS and should be displayed by therapeutic class and preferred term. All prior and concomitant medications taken during the study will be listed for each subject including dosage and indication.

9.3.3. Concomitant and Prior Anti-PD Medications

During the study, patients' concomitant anti-PD medications may be adjusted as needed under the investigator's supervision.

Prior and concomitant anti-PD medications will be coded to a preferred name according to the WHODRUG coding dictionary version 2015:03 or higher. The number and percent of subjects will be summarized for prior and concomitant anti-PD medications for each preferred term (PT) and should be displayed by therapeutic class, chemical/therapeutic/pharmacological subgroup, and preferred term in the FAS. All prior and concomitant anti-PD medications will be listed separately for each subject.

The last dose of anti-PD medication taken the evening before the day when UPDRS part III test are done in defined "ON" state at Screening, Baseline (Pre-dose Day 1), Weeks 2, 6, 12, 24, 36 and 52 will be documented in a subject data listing along with the date and time of UPDRS Part III performed before anti-PD medications. The subject data listing will include medication/treatment, dose, number of tablets or capsules taken, frequency, date of last dose and time of last dose.

9.3.3.1. Total Levodopa Dose

The total levodopa dose at baseline and during the study will be calculated for each subject at each visit and summarized descriptively for each visit in the FAS. A separate listing will also be created listing each subject's calculated total levodopa dose by visit.

9.3.3.2. Total Levodopa Equivalents

The total levodopa equivalent at baseline and during the study will be calculated for each subject at each visit and summarized descriptively for each visit in the FAS. A separate listing will also be created listing each subject's calculated total levodopa equivalent by visit. [Appendix 2](#) contains the rules to calculate levodopa equivalents.

9.4. Demographic and Baseline Characteristics

Demographic and baseline characteristics will be summarized descriptively in the FAS. These variables include:

- Gender
- Race and ethnicity
- Age (years)

- Body weight (kg)
- Height (cm)
- Body Mass Index (BMI) (kg/m²)
- Duration of PD (years)
- Hoehn and Yahr Staging of PD in ON state and OFF state (best estimate)

Age will also be classified into 3 categories (≥ 30 to 54, ≥ 55 to 68 and ≥ 69 to 80 years).

9.5. Medical History Events

Medical conditions resolved by first dose of IMP and ongoing medical conditions will be summarized by MedDRA system organ class (SOC) and PT in the FAS. All medical conditions collected on the eCRF will be included in the listings.

9.6. Exploratory Analyses

All exploratory endpoints will be summarized descriptively in the mFAS.

9.6.1. Exploratory Variables

The exploratory variables including the change from Baseline (where applicable) will be summarized using descriptive statistics by visit:

1. UPDRS Part II (ADL subscale) + Part III (motor subscale) total score
2. UPDRS Part II (ADL subscale) score
3. UPDRS Part III (motor subscale) score in the ON state
4. UPDRS Part I total score
5. UPDRS Part IV total score
6. Dyskinesia as measured by questions 32, 33 and 34 of UPDRS Part IV
7. Motor fluctuations as measured by question 39 of UPDRS Part IV
8. Clinical Global Impression of Improvement (CGI-I)
9. Patient's Global Impression of Improvement (PGI-I)
10. Parkinson's Disease Quality of Life Questionnaire (PDQ-39; total score and individual domain scores)
11. Non-motor Symptom Assessment Scale
12. Patient-completed diaries (Change from Baseline in the number of hours per day spent as follows: OFF, ON time without troublesome dyskinesia, total ON time, ON time with troublesome dyskinesia and asleep time)
13. Healthcare Resource Utilization
14. EuroQol 5D-5L Health Questionnaire (EQ-5D-5L)
15. Fall questionnaire

9.7. Pharmacokinetic Variables

9.7.1. Tozadenant Plasma Concentrations at week 2

Blood samples will be collected for determination of plasma tozadenant concentrations at Week 2.

Plasma concentration data will be presented for all subjects. In all calculations, zero (0 ng/mL) will be substituted for concentration below the quantification limit (BLQ; equivalent to <5 ng/mL) of the assay.

Elapsed time between dosing and plasma sampling will not be tightly controlled and is expected to vary considerably between patients. Summary statistics for tozadenant blood concentrations (number of sample analyzed, number of BLQ values, minimum, and maximum) will be presented on the safety set.

All data collected on the tozadenant blood concentrations will be included in the data listings.

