6.2.4 Visit 3 (Week 2)

Note: Sites participating in Expanded PK Sampling should refer to [Appendix 15.9.2](#) for Week 2 assessments.

Note: Confirm the arrangement for laboratory sample pick-up on the day of the Week 2 visit with the courier (see Central Laboratory Procedures Manual).

1. For all applicable patients: Verify continuation of (or any change to) contraceptive method since Screening and document.
2. Obtain sample for the following laboratory tests and record the date and time of collection:
 - a. PK blood sample(s) for plasma tozadenant concentration.
 - i. Sparse PK Sampling: Collect one (1) PK blood sample at the most convenient time during the visit. Record the patient-reported date and approximate time when the patient took the most recent dose of IMP. Record the date and time of PK sample collection.
 - ii. Expanded PK Sampling (Select Sites Only): Sites participating in Expanded PK Sampling should refer to [Appendix 15.9.2](#).

Note: For processing, labeling and shipping of samples, follow the instructions provided in the Central Laboratory Procedures Manual.

- b. Hematology and chemistry (inclusive of liver function tests).
- c. TSH, free T3, and free T4.
- d. For females of childbearing potential: urine pregnancy test.
- e. Urinalysis.

Note: For processing, labeling and shipping of samples, follow the instructions provided in the Central Laboratory Procedures Manual.

3. Assess AEs by asking open-ended queries and record the assessments.
4. Record concomitant medication use; assess and record any changes to anti-PD medication dose or regimen.
5. Obtain and record BP and pulse measurements after at least 5 minutes supine rest and again after standing for approximately 1 and 3 minutes.
6. Obtain 12-lead ECG. Ensure the ECG is collected when the patient is not experiencing dyskinesia that would interfere with an adequate recording. Assess any changes from Baseline for clinical significance.
7. Record the date and approximate time of the most recent dose of levodopa taken prior to the UPDRS assessment.
8. Perform the following assessments in the ON state:
 - a. Perform full UPDRS Parts I, II, III (motor) and IV. UPDRS Part III should be performed approximately 1 to 3 hours after the patient has taken a scheduled dose of levodopa (preferably their morning dose of levodopa). UPDRS in the ON state will be measured at a time representative of the ON state in that patient, not in “best” ON.
 - b. Administer the following assessments:

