15.9 Expanded Pharmacokinetic Sampling Procedures – Applicable to Select Sites Only

For those subjects who have consented to participate in the expanded tozadenant PK sampling, [Sections 15.9.1](#) and [15.9.2](#) should be referred to instead of [Sections 6.2.3.4](#) (Baseline Assignment and Dispensing and Investigational Medicinal Product) and [6.2.4](#) (Visit 3/Week 2), respectively.

Pharmacokinetic blood samples for determination of plasma tozadenant concentration will be collected at the Week 2 study visit at select sites only. The Schedule of Events for subjects participating in Expanded PK Sampling is provided in [Table 4](#).

15.9.1 Baseline (Visit 2) Assignment and Dispensing and Investigational Medicinal Product for Subjects Participating in Expanded PK Sampling (Replacement Section for [Section 6.2.3.4](#))

1. For patients meeting all entry criteria, complete the IMP assignment transaction using the IXRS by following the procedures provided.
 - a. Dispense the open-label IMP bottle(s) assigned by the IXRS to the patient for this study visit. Each bottle consists of either 50 tablets of 120 mg tozadenant or 100 tablets of 60 mg tozadenant.
 - b. Record the date IMP was dispensed in IMP dispensing records including patient number, assigned IMP bottle number(s), and date and time IMP was dispensed.
 - c. Review the dosing instructions for the IMP with the patient, answer any questions, and remind the patient to return the IMP (including all used, unused and partially used bottles) at the next visit.
 - d. Patients will be instructed to take either two (2) 60 mg tablets or one (1) 120 mg tablet of the dispensed IMP by mouth twice daily (BID), in the morning and in the evening preferably at the same time each day, for a total of either two (2) 120 mg tablets or four (4) 60 mg tablets per day. The evening dose should be approximately 12 hours after the morning dose. Patients will be instructed to take their morning and evening doses 1 hour before or 2 hours after a meal and to refrain from eating for 1 hour after dosing. Patients should take the first dose of IMP at home after the Baseline Visit.
2. Instruct the patient to take the first dose of IMP at home on the evening of dispensation.
3. Ensure that the patient understood the dosing instructions and the use of the extra doses included in the bottle if visit delayed and/or use of visit window.

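### The Week 2 sparse PK samples are summarised only by n, BLQ count, minimum and maximum, and the recorded dose and sample times enter no planned summary or plot of them

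*SAP*

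**What the plan says.** Protocol 6.2.4 (Week 2) sets the sparse procedure: "Collect one (1) PK blood sample at the most convenient time during the visit". It then asks sites to do two things: "Record the patient-reported date and approximate time when the patient took the most recent dose of IMP", and "Record the date and time of PK sample collection".

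SAP 9.7.1 gives the handling. In all calculations, "zero (0 ng/mL) will be substituted for concentration below the quantification limit (BLQ; equivalent to <5 ng/mL) of the assay". It warns that "Elapsed time between dosing and plasma sampling will not be tightly controlled and is expected to vary considerably between patients", and goes straight on to the planned output: "Summary statistics for tozadenant blood concentrations (number of sample analyzed, number of BLQ values, minimum, and maximum) will be presented on the safety set". It closes with "All data collected on the tozadenant blood concentrations will be included in the data listings".

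Three other places bear on the point:

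- Protocol 15.9 gives a separate Week 2 procedure, with a trough sample and an on-site dose, to a subset at select sites: "For those subjects who have consented to participate in the expanded tozadenant PK sampling". They follow it instead of the sparse procedure. The size of the subset is not given.
- SAP 9.7.2 summarises that subset fully: mean, SD, CV%, median, range and geometric statistics at trough and at 3, 5, 6 and 8 hours, plus Cmax, tmax and AUC0-last, using actual times.
- Protocol 3.1 starts everyone on 120 mg BID and allows dose changes only from Week 2. By plan, dose is therefore uniform up to this sample.

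**The concern.** The SAP's stated reason for the short summary is uncontrolled time since dose. That is a sound argument against one pooled mean. It does not support minimum and maximum instead, because the two extremes are fully exposed to the same timing variation. Nor does it explain leaving the times out of the summary, since the protocol has sites record what is needed to derive time since dose.

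Tozadenant concentration at Week 2 is a listed variable in Protocol 11.2.2 and SAP 4.3. The planned table cannot show a typical concentration for patients outside expanded PK, or how concentration falls with time since dose. If any sample is BLQ, the minimum carries no information beyond the BLQ count printed beside it.

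**Working it through.** **Inputs.** Planned enrolment is 450 (Protocol 11.9, SAP 3.2). The BLQ limit is 5 ng/mL, with BLQ set to 0 (SAP 9.7.1). The documents give no BLQ rate, half-life or expected concentration, so the BLQ rate p is an assumption and is shown over a range.

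**The plan's own figure.** 450 / (1 − 0.30) = 642.9, rounded up to 643, against about 645 screened as stated. This agrees. The 450 is an upper bound on sparse samples, because expanded-PK participants and patients who leave before Week 2 give none.

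**Chance that the reported minimum is 0.** One BLQ value is enough, so, treating samples as independent, the chance is 1 − (1 − p)^n. The n = 360 column is an assumed smaller number of sparse samples.

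| Assumed BLQ rate p | n = 450 | n = 360 |
|---|---|---|
| 0.01% | 4% | 4% |
| 0.05% | 20% | 16% |
| 0.1% | 36% | 30% |
| 0.2% | 59% | 51% |
| 0.5% | 90% | 84% |
| 1% | 99% | 97% |

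Worked example: p = 0.002 and n = 450 give 1 − 0.998^450 = 0.594. Solving for p at n = 450, a rate of about 0.15% gives an even chance and about 0.66% gives 95%.

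**What the four statistics cannot show.** Take two invented sets of 450 values:

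- Set A: one 0, 224 values of 100, 224 of 200, one 2000. The median is (100 + 200)/2 = 150.
- Set B: one 0, 224 values of 1000, 224 of 1500, one 2000. The median is (1000 + 1500)/2 = 1250.

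Both give n = 450, BLQ = 1, minimum 0 and maximum 2000, so the planned table would be identical. This does not depend on the BLQ rate: the median is equally invisible when the minimum is a measured value.

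**Use of the times.** SAP 9.7.1 defines no time-since-dose variable, time window, concentration-by-time plot or model. Actual times are called for only in SAP 9.7.2. In the text available, neither document plans a population PK or exposure-response analysis that would use the sparse samples.

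**The case against.** The restriction looks deliberate. Timing is uncontrolled, the dose times are patient-reported and approximate, and the SAP puts its full statistics where timing is controlled. Protocol 11.6 promises only a descriptive report of the assay results, and SAP 9.7.1 meets that. PK is in neither the objectives nor the endpoint lists. All of this stands. It makes the point an improvement rather than the correction of an error, but it does not explain why recorded times enter no summary.

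Four stronger readings are tempting, and the documents do not support them.

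- A reader might infer that the plan says nothing about typical exposure. SAP 9.7.2 describes it in detail for trial patients at the same visit. The gap concerns patients outside that subset.
- A reader might infer that every patient gives a sparse sample. Protocol 15.9 replaces the sparse procedure for expanded-PK participants.
- A reader might infer that the times, or the data, are discarded. All concentration data are listed, and the times would reasonably appear there, although SAP 9.7.1 does not name them. What is missing is a summary or plot that uses them.
- A reader might infer that a zero minimum is nearly certain. Patients are told to take their study drug before arriving (Protocol 6.1), so very low BLQ rates are plausible and the chance could be a few per cent. A zero would not mislead either, because the BLQ count stands next to it.

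**Conclusion.** The point holds as a cheap improvement. For at most about 450 sparse samples, the plan reports two extremes and two counts, makes no summary use of the recorded times, and leaves typical exposure to be described only in an expanded-PK subset of unstated size at select sites.

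The chance that the minimum is an imputed 0 runs from about 4% to 99% with 450 samples, for assumed BLQ rates from 0.01% to 1%. The documents do not allow that range to be narrowed. The case for change rests on the missing centre and the unused times, which do not depend on it. The output is descriptive, and the primary safety analysis is unaffected.

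**What to change.** In SAP 9.7.1:

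1. Derive time since last dose from the recorded dose and sample times.
2. Add a scatter plot of concentration against time since dose, with BLQ samples marked.
3. Tabulate n, number BLQ, median and quartiles over all samples in wide windows fixed in advance, for example 0–2, >2–4, >4–8, >8–12 and >12 h. Rank BLQ values lowest, and print <5 ng/mL if a quantile falls among them.
4. Report the minimum quantifiable value beside the BLQ count.
5. Show any geometric mean of quantifiable values only beside the BLQ count, because dropping BLQ samples biases it upward.

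The cost is SAP wording, one derived variable, one table and one figure. It needs no new data and no protocol amendment. The downside is that the reported dose times are approximate, so the windows must be wide and those far from the usual visit timing may hold few samples.

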9.7.2. Tozadenant expanded PK

9.7.2.1. Tozadenant expanded PK Plasma concentration

Plasma concentration for the expanded PK will be described using the PK population.

For expanded PK blood samples for plasma concentration, one pre-dose/trough PK sample will be collected prior to the administration of tozadenant. After the administration of tozadenant, four additional samples will be collected at 3, 5, 6 and 8 hours.

Trough concentration will be summarized in terms of n, arithmetic mean, SD, arithmetic CV%, median, minimum, maximum, geometric mean and geometric CV%. The plasma concentration at 3 hours, 5 hours, 6 hours, and 8 hours will be described similarly. Values that are BLQ will be set to zero when calculating the aforementioned descriptive statistics. If one or more of the concentration values in a data series is zero, the geometric mean and geometric CV% will not be calculated and will be denoted as NC.

Concentrations will be listed to the same degree of accuracy as supplied by the bioanalytical laboratory. As well, units of concentration will be presented as they are received from the bioanalytical laboratory.

Individual plasma concentration-time profiles and individual concentration listings will be presented using actual sampling times. Arithmetic mean plasma concentration-time profiles will be plotted on linear and semi-logarithmic scales.

9.7.2.2. Tozadenant expanded PK Pharmacokinetic parameters

Pharmacokinetic parameters for the expanded PK will be described using the PK population.

The following pharmacokinetic parameters for tozadenant will be calculated using non-compartmental analysis using Phoenix WinNonlin Version 6.4 or higher:

Parameter	Definition
------------------	-------------------

AUC _{0-last}	Area under the concentration-time curve from time 0 to the last measurable concentration, as calculated by the trapezoidal method.
-----------------------	--

C_{\max}	Maximum plasma concentration
t_{\max}	Time of maximum measured plasma concentration (C_{\max})

Additional pharmacokinetic parameters may be determined where appropriate.

Pharmacokinetic analysis will be carried out using actual postdose times recorded in the raw data. If actual times are missing, nominal times may be used.

C_{\max} and t_{\max} will be obtained directly from the plasma concentration-time profiles. If C_{\max} occurs at multiple timepoints, the earliest time will be used for t_{\max} .

C_{\max} and $AUC_{0-\text{last}}$ will be summarized in terms of n, arithmetic mean, SD, arithmetic CV%, median, minimum, maximum, geometric mean and geometric CV%. For the parameter t_{\max} , the descriptive statistics will include n, arithmetic mean, SD, minimum, median, and maximum.

9.7.2.2.1. Criteria for handling concentrations below the limit of quantification in Pharmacokinetic analysis

Concentration values that are below the level of quantification (BLQ) will be set to zero, with defined exceptions as follows;

- Any embedded BLQ value (between 2 quantifiable concentrations) and BLQ values following the last quantifiable concentration in a profile will be set to missing for the purposes of PK analysis.
- If an entire concentration-time profile is BLQ, the profile will be excluded from the PK analysis.
- If a predose concentration is missing, these values will be set to zero.

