3. STUDY DESIGN

This is a Phase 3, international, multicenter, open-label study in levodopa-treated patients with PD experiencing end-of-dose “wearing-off”. This study includes a Screening Period of up to 6 weeks that starts with a Screening Visit, followed by a 52-week Open-Label Treatment Period and a Safety Follow-Up Visit 4 weeks after completion of investigational treatment. After providing written informed consent, patients will undergo screening evaluations. Patients must meet all inclusion criteria and none of the exclusion criteria and they must successfully complete the diary training and achieve 80% overall diary concordance with the PD diary trainer/rater including at least 1 OFF interval to be considered for enrollment. If preliminary eligibility is confirmed by the investigator, patients will then be scheduled for a Baseline Visit and will be required to return a valid set of Baseline diaries. Final eligibility will be determined at the Baseline Visit.

Patients will return to the study site for evaluation at scheduled visits at Weeks 2, 6, 12, 24, 36, and 52. Patients will be contacted by telephone before the start of each 3-day PD diary completion period to be reminded to complete the diary. A final Safety Follow-Up Visit (Week 56) will occur 28 ± 3 days after the patient’s last open-label dose of tozadenant. Upon starting study treatment, patients will receive open-label tozadenant at a dose of 120 mg BID. Adjustments to the open-label tozadenant dose are allowed to be made by the investigator starting at Week 2 and at any of the subsequent visits. Doses of 60 or 120 mg BID are permitted; the investigator may adjust a patient’s dose to either level as clinically indicated. The Interactive Response System (IXRS) will be used to assign, track and manage the tozadenant inventory at each study site.

The Schedule of Events/Evaluations for is shown below in [Table 1](#).

Table 1: Schedule of Events/Evaluations

Assessments	Study Period	Baseline	Open-Label Treatment						Safety	Early	Unscheduled
	Screening ^a	Predose	(52 weeks)						Follow-Up	Termination ^w	
	Study Week ^b	BL	2	6	12	24	36	52	56		
Study Visit	-6 to -1		(± 3 d)	(± 3 d)	(± 3 d)	(± 7 d)	(± 7 d)	(± 14 d) [16 weeks]	(28 ± 3 d after last dose of IMP)		
	V1	V2	V3	V4	V5	V6	V7	V8	V9		
Written Informed Consent	X										
Demographics and Medical History, including neurological and PD history	X										
Recording of concomitant and anti-PD medications	X	X	X	X	X	X	X	X	X	X	X

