3.1.4. Expanded PK Population (xPK)

The xPK Population will consist of all subjects with expanded PK and for whom there are adequate samples collected to provide analyzable PK data.

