9. STATISTICAL METHODS

The software used for all summary statistics and statistical analyses will be SAS[®] (SAS Institute, Inc.)¹ Version 9.2 or later.

Most continuous data will be summarized with the following descriptive statistics: number of observations, mean, SD, median, minimum, and maximum; interquartile ranges will be provided as appropriate. Categorical data will be summarized with frequencies and percentages.

Missing data will not be imputed.

Formal statistical tests will be not be conducted and thus no p-values will be reported.

For presentation of data, the mean and median will be presented to 1 decimal place greater than the original data, SD will be to 2 decimal places greater than the original data, and the minimum and maximum will have the same number of decimal places as the original data. The format for range will be “Min, Max”. Standard deviation will be abbreviated as “SD”.

Data that is collected in an early termination visit may be included in the calculation of summary statistics for the week the early termination visit falls into, as long as the visit falls within the time-frame of a scheduled visit as displayed in [Table 1](#). For example, if a subject has early termination visit 3 days prior to a previously scheduled week 12 visit, the data collected will be included in the calculation of summary statistics for week 12. If the diary data is collected from the site at this visit, the diary data would also be included in the calculation of summary statistics for week 12. If data is included for a study week as in this example above, it would not be included as part of the ‘early termination column’s’ summary statistics, i.e., data would only be used and included once in a summary statistic calculation, i.e., used only in calculation of summary statistics for week 12 in this example.

For certain variables (i.e., ESS, UPDRS III), subjects should complete these at the site during an “ON” state, per the protocol. The site should have only collected this data if the subject was in fact in the “ON” state. However, in cases where the site collected the data anyway (i.e., in “OFF” or “fluctuating”), we will treat all data that shows up in the database as if they followed the protocol, i.e., we will not check for the subject being in the “ON” state before including in summary statistics.

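### A missing Week 2 predose concentration is set to zero although it is a trough on repeated dosing; under a linear trapezoid this lowers AUC0-last in that profile whenever the trough is quantifiable

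*SAP*

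**What the plan says.** SAP 9.7.2.2.1 sets BLQ concentrations to zero in the PK analysis and lists exceptions. The last bullet concerns a missing value, not a BLQ one, and carries no condition: "If a predose concentration is missing, these values will be set to zero".

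SAP 9.7.2.2 defines AUC0-last from time 0 by a trapezoidal method without naming the variant, and adds that "Pharmacokinetic analysis will be carried out using actual postdose times recorded in the raw data".

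On sampling, SAP 9.7.2.1 states that "one pre-dose/trough PK sample will be collected prior to the administration of tozadenant" and that, after dosing, "four additional samples will be collected at 3, 5, 6 and 8 hours".

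On dosing, SAP 3 states: "Upon starting study treatment, patients will receive open-label tozadenant at a dose of 120 mg BID". Protocol 15.9.1 and 15.9.2 place the expanded profile at Week 2 and hold only the visit-day dose until the predose sample is drawn.

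SAP 9.7.1 gives the assay limit: "below the quantification limit (BLQ; equivalent to <5 ng/mL) of the assay". SAP 3.1.4 admits to the xPK population subjects "for whom there are adequate samples collected to provide analyzable PK data", without defining adequacy.

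**The concern.** Zero is a sensible stand-in before a first dose, when no drug is on board. This study has no first-dose profile. By Week 2 patients have taken the drug twice daily for about two weeks, the SAP itself treats the predose sample as a trough, and it plans a full descriptive summary of troughs. A missing trough is therefore an unknown concentration that may well be above the assay limit.

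The inserted zero is the left end of the first trapezoid, which is 3 h wide because nothing is sampled between dosing and 3 h. If the true trough is quantifiable and the trapezoid is linear, every affected profile errs in the same direction, so the error does not average out across patients. What is at stake is a modest understatement of reported exposure.

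**Working it through.** The documents state no AUC, trough, half-life or number of expanded-PK subjects, so there is no figure of the plan's own to reproduce.

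**Inputs from the documents.** Nominal times 0, 3, 5, 6 and 8 h (SAP 9.7.2.1); assay limit 5 ng/mL (SAP 9.7.1); AUC0-last by trapezoid from time 0 (SAP 9.7.2.2); missing predose value = 0 (SAP 9.7.2.2.1).

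**Step 1: loss in one profile, linear trapezoid.** Let C0 be the true trough and C3 the 3 h value.
- First interval with the true trough: 3 x (C0 + C3)/2.
- First interval under the rule: 3 x (0 + C3)/2.
- Difference: 1.5 h x C0. At C0 = 5 ng/mL this is 7.5 ng·h/mL; at C0 = 100 ng/mL it is 150 ng·h/mL.

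Linear-up/log-down gives the same loss when C0 is no higher than C3, because the first interval is then still linear. With actual times the factor is half the first interval: 1.25 h if the first sample is at 2.5 h, 1.75 h if at 3.5 h, and 2.5 h if the 3 h sample is missing and the next is at 5 h.

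**Step 2: relative loss.** Write C0 as a fraction f of the 0-8 h average concentration, AUC/8. The loss is 1.5 x f/8 = 0.1875 x f:

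| f | Loss in AUC0-last |
|---|---|
| 0.10 | 1.9% |
| 0.50 | 9.4% |
| 0.90 | 16.9% |

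**Step 3: if the trough is BLQ.** The general BLQ rule also gives zero, so nothing changes.

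**Step 4: dependence on the trapezoid variant.** With a log trapezoid on the rising limb as well, the first interval with the true trough is 3 x (C3 - C0)/ln(C3/C0). With C0 = 0 a log rule cannot be computed and falls back to linear, giving 1.5 x C3. At C0/C3 = 0.1 the true-trough area is 3 x 0.9/ln(10) = 1.17 x C3, against 1.50 x C3 under the rule, so the rule raises AUC. The two are equal where (1 - r)/ln(1/r) = 0.5, at r = C0/C3 of about 0.20. Above that ratio the rule lowers AUC under this variant too.

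**Step 5: illustrative size (assumed model).** One-compartment oral steady state, 12 h interval, half-life 2 to 24 h, absorption rate 0.5 to 2 per h, linear trapezoid:

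| Hours since last dose | Smallest loss (half-life 2 h, ka 2) | Largest loss (half-life 24 h, ka 0.5) |
|---|---|---|
| 12 | 1.7% | 16.4% |
| 13 | 1.2% | 16.3% |
| 14 | 0.8% | 16.2% |
| 16 | 0.4% | 15.9% |

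The predose value never exceeded 0.83 of the highest post-dose sample, so Cmax and tmax did not change.

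**Step 6: effect on the mean.** If missingness is unrelated to AUC, the change in the mean is the share affected x the loss per profile. With assumed shares of 5% to 20%, it runs from 5% x 0.4% = 0.02% to 20% x 16.4% = 3.3%.

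**The case against.** - **The direction is not unconditional.** A reader might infer that the rule always lowers AUC0-last. The documents do not support that: the trapezoid variant is not named, and Step 4 shows a reversal. Linear is the natural reading and logging the rising limb is unusual, so this limits the claim without removing it.
- **No contradiction with the general missing-data rule is needed.** A reader might infer that the bullet breaches SAP 9, which says "Missing data will not be imputed". That sentence is a general default, and the SAP makes specific exceptions elsewhere: missing AE relationship and severity (5.11), unknown AE start dates (5.12) and missing medication stop dates (5.9, 5.10). A specific PK exception fits that pattern. The objection to zero rests on its being the wrong value for a trough.
- **It may seldom apply.** The predose sample is a supervised clinic step, and a profile without it could be left out as inadequate under SAP 3.1.4. Parts of the protocol's expanded-sampling text are redacted, so instructions on missed samples cannot be seen. This stands as a limit on size. SAP 3.1.4 permits exclusion but does not require it, and the bullet presupposes that some such profiles are analysed.
- **Sparse sampling may matter more.** In the Step 5 model the linear trapezoid with the true trough already understates the 0-8 h area by 1% to 37%. With a 2 h half-life and ka 2, at 12 h since the last dose, the shortfall is 36% without the rule and 37% with it. With 24 h and ka 0.5 it goes from 1% to 17%. So the rule dominates only when the half-life is long.
- **Dropping profiles can cost more than the bias.** With 10% affected and the largest bias (1.6%), zero has the smaller mean squared error unless the standard error of the mean is below about 1.64%/sqrt(1/0.9 - 1) = 4.9%, which is about 66 profiles at an assumed CV of 40%. With 20% affected the threshold is 6.6%, about 37 profiles. The number of expanded-PK subjects is not readable, so the fix is not shown to improve the mean on that criterion. It does avoid reporting an AUC0-last built on an invented value.

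**Conclusion.** The point holds as a minor one. Zero is not a defensible value for an unknown trough at Week 2 on twice-daily dosing, and the bullet applies it without condition. Under a linear or linear-up/log-down trapezoid, with a trough of at least 5 ng/mL, nominal times and the 3 h sample present, AUC0-last in that profile falls by 1.5 h x trough.

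That conditional statement is secure; the size is not. Half-life, absorption rate, trough level and share missing are all assumptions. Within the ranges tried, the loss is about 0.4% to 16% per affected profile and 0.02% to 3.3% in the group mean.

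A reader might also infer that the trial's safety findings are at risk. They are not: the rule touches one descriptive PK parameter in a subset, the study makes no formal tests, and Cmax and tmax change only if the missing predose value would have been the highest in the profile.

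**What to change.** Replace the last bullet of SAP 9.7.2.2.1 with:

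*A missing predose concentration at Week 2 is left missing; AUC0-last is not reported for that profile (a partial AUC3-8h may be listed); Cmax and tmax use the observed samples.*

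Predose samples that were assayed and found BLQ stay at zero under the existing general rule.

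**Cost.** One SAP bullet, with no change to visits, dosing or sampling. A few profiles lose AUC0-last. The standard error of its mean rises by the factor 1/sqrt(1 - share): 2.6%, 5.4% or 11.8% if 5%, 10% or 20% of profiles are affected (assumed). If missing samples are related to exposure, leaving those profiles out could cause some selection; listing the partial AUC3-8h lets a reader check for it.
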